8.1.4 Serious Adverse Drug Reaction (SADR)

- An adverse drug reaction (ADR) is an adverse event for which a causal relationship (Possible/Probable
- relation) between the study drug and the occurrence of the event is suspected. The ADR should be
- 1013 classified as **serious** if it meets one or more of the seriousness criteria.

1014	8.1.4.1	Reported serious adverse events/reactions related to study drug	
1015		Potential Risk of Thyroid C-Cell Tumors	
1016		Acute Pancreatitis	
1017		Acute Gallbladder Disease	
1018		Risk for Hypoglycemia with Concomitant Use of Anti-Diabetic Therapy	
1019		Heart Rate Increase	
1020		Renal Impairment	
1021		Hypersensitivity Reactions	
1022		Suicidal Behavior and Ideation	
1023	8.1.5	Severity Assessment Definitions	
1024		 Mild: Transient symptoms, no interference with the subject's daily activities 	
1025		 Moderate: Marked symptoms, moderate interference with the subject's daily activities 	
1025		 Severe: Considerable interference with the subject's daily activities, unacceptable 	
1027	8.1.6	Relationship to Study Drug Assessment Definitions	
1028		• Probable: Good reasons and sufficient documentation to assume a causal relationship	
1029		Possible: A causal relationship is conceivable and cannot be dismissed	
1030		• Unlikely: The event is most likely related to an etiology other than the trial product	
1031	8.1.7	Outcome Categories and Definitions	
1032		• Recovered: Fully recovered or by medical or surgical treatment the condition has returned to	
1033		the level observed at the first trial related activity after the subject signed the informed	
1034		consent	
1035		• Recovering: The condition is improving and the subject is expected to recover from the event.	
1036		This term should only be used when the subject has completed the trial	
1037		• Recovered with sequelae: As a result of the AE, the subject suffered persistent and significant	
1038		disability/incapacity (e.g. became blind, deaf, paralysed). Any AE recovered with sequelae	
1039		should be rated as an SAE	
1040		Not recovered	
1041		• Fatal	
1042		• Unknown	
1043		8.2 Collection, Recording and Reporting of Adverse Events	
1044	8.2.1	Collection and Recording of Adverse Events	
1045	All eve	nts meeting the definition of an adverse event must be collected and reported from the first trial	
1046	related activity after the subject has signed the informed consent and until the end of the post-treatment		
1047	follow-	up period as stated in the protocol.	
1048			
1049		a contact with the subject, the investigator must seek information on adverse events by specific	
1050		ning and, as appropriate, by examination. Information on all adverse events should be recorded	
1051		iately in the source document, and also in the appropriate adverse event module of the case report	
1052	Torm (CRF) All clearly related signs, symptoms, and abnormal diagnostic procedures results should	

treatment follow-up is defined as 30 days following the last administration of study treatment.

The study period during which adverse events must be reported is normally defined as the period from the

initiation of any study procedures to the end of the study treatment follow-up. For this study, the study

recorded in the source document, though should be grouped under one diagnosis.

1053 1054 1055

1056

- 1059 All adverse events occurring during the study period must be recorded. The clinical course of each event
- 1060 should be followed until resolution, stabilization, or until it has been determined that the study treatment
- 1061 or participation is not the cause. Serious adverse events that are still ongoing at the end of the study
- period must be followed up to determine the final outcome. Any serious adverse event that occurs after 1062
- the study period and is considered to be possibly related to the study treatment or study participation 1063
- 1064 should be recorded and reported immediately.

1065 **8.2.1.1** Preexisting Condition

- 1066 A preexisting condition is one that is present at the screening of the study. A preexisting condition should
- be recorded as an adverse event if the frequency, intensity, or the character of the condition worsens 1067
- 1068 during the study period.

1069 8.2.1.2 General Physical Examination Findings

- 1070 At screening, any clinically significant abnormality should be recorded as a preexisting condition. At the
- end of the study, any new clinically significant findings/abnormalities that meet the definition of an 1071
- 1072 adverse event must also be recorded and documented as an adverse event.

1073 **8.2.1.3** Abnormal Laboratory Values

- 1074 A clinical laboratory abnormality should be documented as an adverse event if any one of the following 1075 conditions is met:
 - The laboratory abnormality is not otherwise refuted by a repeat test to confirm the abnormality
 - The abnormality suggests a disease and/or organ toxicity
 - The abnormality is of a degree that requires active management; e.g. change of dose, discontinuation of the drug, more frequent follow-up assessments, further diagnostic investigation, etc.

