4.6 Early Withdrawal of Subjects

4.6.1 When and How to Withdraw Subjects

- If a subject is not able to tolerate the study drug, the subject will be removed from the study.
- If a subject decides to withdraw from the study, the subject will be removed from the study.

- If the PI believes that it is in a subject's best interest to discontinue participation, the subject will be removed from all remaining study requirements.
 - A subject may be withdrawn from the study at the discretion of the PI due to a safety concern or if judged non-compliant with trial procedures.

If a subject fails to return for one scheduled study visits, the Investigator will attempt to contact the subject to determine and document the reason the subject has failed to return and to encourage compliance with the study visit schedule. Before a subject can be considered lost to follow-up, a minimum of 2 phone calls at different times of the day and a certified letter are required. All of these contact attempts will be documented in the source documents.

In case of withdrawal from the study, the appropriate follow-up care will be provided for those cases, including hospital and clinic follow-up when necessary.

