
Blood Pregnancy (Total Beta Quantitative HCG) (Only applicable for women of childbearing

882

883

potential)

- 884 **BMP**
- 885 HbA1c
- Lipid profile 886
- 887 Amylase
- Lipase 888
- 889 Additional 15 ml blood for future analyses - Banking of additional plasma and serum for future markers of caridometabolic risk in post-RYGB patients (6 and 12 months only). 890

891 6.2.5 **Questionnaires**

- 892 PHO-9
- 893 **IPAQ**

894 6.2.6 **Adverse Events Assessment**

- 895 Through-out the study the occurrence of drug-related AEs and pregnancies will be monitored, recorded,
- and reported to IRB and Novo Nordisk. 896

897 **Monthly Contact** 6.2.7

- 898 Study staff will call or email each subject at 1, 2, 4, 5, 7, 8, 10, and 11 months to review medication compliance and 899 adverse events.
 - 7 Statistical Plan

7.1 **Sample Size Determination**

We intend to recruit 132 subjects. A recent study of liraglutide versus placebo in subjects weighing 106.2 \pm +/- 21.1 kg (BMI 38.2 \pm 6.4) at baseline demonstrated that nearly 2/3 of subjects treated with liraglutide for 56 weeks lost at least 5% of enrollment body weight, vs. approximately 1/4 with placebo. We expect to see similar results in our subjects. In order to detect an absolute difference of 36.1% in the proportion of subjects losing at least 5% of enrollment body weight in the liraglutide (expected proportion 63.2%) and placebo arms (expected proportion 27.1%), with an alpha of 0.05 and beta of 0.1, we will require a sample size of 99 (2x liraglutide: 1x placebo). In order to account for an estimated loss-to-follow-up of 25%, we increase the sample size to 132.

7.2 **Statistical Methods**

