1429 12 Study Finances 1430 12.1 Funding Source 1431 This study will be financed by Novo Nordisk. 1432 12.2 Conflict of Interest 1433 Any investigator who has a conflict of interest with this study (patent ownership, royalties, or financial 1434 gain greater than the minimum allowable by their institution, etc.) must have the conflict reviewed by a properly constituted Conflict of Interest Committee with a Committee-sanctioned conflict management 1435 plan prior to participation in this study. All NYULMC investigators will follow the applicable University 1436 conflict of interest policies. 1437 1438 12.3 Costs to the Subject 1439 There is no cost for the research related components (study drugs, visits, tests, procedures). 1440 12.4 Subject Stipends or Payments 1441 For their participation in each aspect of the study, patients will be paid in gift cards up to \$500 for their time and travel expenses. The subjects will receive a gift card for each completed visit according to the 1442 below schedule. The subjects will receive a matching gift card if the visit is completed within the time 1443 1444 below. 1445 • \$50 - Visit 2 (3 month +/- 4 weeks from the first day of study drug) \$50 - Visit 3 (6 months +/- 4 weeks from the first day of study drug) 1446 \$50 - Visit 4 (9 months +/- 4 weeks from the first day of study drug) 1447 1448 • \$100 - Visit 5 (12 months +/- 4 weeks from the first day of study drug) 1449 13 Publication Plan Once the data analysis is complete the data will then be prepared for publication in a peer reviewed 1450 1451 journal deemed appropriate by Novo Nordisk and PI or otherwise disclose publicly the data or results of 1452 this study. The study information will be registered at clinicaltrials.gov. 1453 Neither the complete nor any part of the results of the study carried out under this protocol, nor any of the information provided by Novo Nordisk for the purposes of performing the study, will be published or

1454 1455 passed on to any third party without the consent of Novo Nordisk. Any investigator involved with this 1456 study is obligated to provide Novo Nordisk with complete test results and all data derived from the study. 1457

1458

1459

1460 1461

PI will provide Novo Nordisk with a manuscript of submission(s) for review and comment. PI will not publish any manuscript without Novo Nordisk's prior approval.

1462

14 References

1463 1464

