	15.1 Attachment 1- Study Procedures
	15.2 Attachment 2- PHQ (Patient Health Questionnaire)
	15.3 Attachment 3- International Physical Activity Questionnaire (IPAQ)
	15.4 Attachment 4- 24 hours Food Recall
	15.5 Attachment 5- Diet and Exercise Diary with Preferred Starches List

ATTACHMENT 1

ATTACHMI Visit Number	1			2			3			4			5
(1010 1 (MIII	Baseline	1M	2M	3	4M	5M	6	7M	8M	9	10M	11M	12
				months			months			months			months
	0-4 wks prior to												
Visit window	the			± 4 wks			± 4 wks			± 4 wks			± 4 wks
	treatment												
Informed													
consent	X												
Screening	X												
Demographics	X												
Medical	X												
History	71												
Weight, BP,													
HR, Waist &	X			X			X			X			X
Neck													
Circumference	V												
Height	X X			X			X			X			X
Medications Blood	Λ			Λ			Λ			Λ			Λ
Pregnancy													
Test (Beta													
Quantitative													
HCG) (Only	X			X			X			v			X
applicable	Λ			Λ			Λ			X			Λ
for women of													
childbearing													
potential) ¹ BMP,													
HbA1c, ¹ Lipid													
profile,	X			X			X			X			X
Amylase,	Α			Λ			Λ			Λ			Λ
Lipase													
Additional													
plasma and													
serum for	X						X						X
future													
analyses													
PHQ-9, IPAQ,													
24 hr diet	X			X			X			X			X
recall													
Diet and													
Physical	37			37			3.7			37			37
Activity	X			X			X			X			X
Counseling by													
RD Body													
Composition Composition	X			X			X			X			X
Comorbidities:													
Diabetes,													
Hypertension,	X			X			X			X			X
STOP-BANG													

² AEs	X	X	X	X	X	X	X	X	X	X	X	X	X
Study Medication Compliance Phone call		X	X		X	X		X	X		X	X	

1. Fasting is required

2. Ask about hypoglycemia symptoms for patients with Type 2 DM

Universal Trial Number: U1111-1178-7319

1530

1531 ATTACHMENT 2:

1532 15.4.1.1 PHQ-9 (Patient Health Questionnaire Nine Symptom Checklist)

1533

Name	>	Da	nte	
Over the last 2 weeks , how often have you been bothered by any of the following problems?	Not at all	Several days	More than half the days	Nearly every day
1. Little interest or pleasure in doing things	0	1	2	3
2. Feeling down, depressed, or hopeless	0	1	2	3
3. Trouble falling or staying asleep, or sleeping too much	0	1	2	3
4. Feeling tired or having little energy	0	1	2	3
5. Poor appetite or overeating	0	1	2	3
6. Feeling bad about yourself—or that you are a failure or have let yourself or your family down	0	1	2	3

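### Section 6.2.6 ties adverse event recording to drug-related events, against section 8.2.1 and the any-event safety endpoint, and no contact is scheduled for the 30 days after the last dose

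*Combined protocol and SAP*

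**What the plan says.** Section 8.2.1 sets a wide rule. Collection starts at the first trial "related activity after the subject has signed the informed consent and until the end of the post-treatment" follow-up period, and the length of that period is fixed: "treatment follow-up is defined as 30 days following the last administration of study treatment". Within it, "All adverse events occurring during the study period must be recorded", with no condition on causality. Events are found by asking: at "a contact with the subject, the investigator must seek information on adverse events by specific" questioning.

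The contacts at which staff can ask are these. Section 6.2.7 states: "Study staff will call or email each subject at 1, 2, 4, 5, 7, 8, 10, and 11 months to review medication" compliance and adverse events. The last visit, as timed in section 12.4, is "Visit 5 (12 months +/- 4 weeks from the first day of study drug". The schedules in section 6 and Attachment 1 both end at that visit, and their row "Study Medication Compliance Phone call" has its last mark at month 11.

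For early stoppers, section 4.6.1 says: "If a subject is not able to tolerate the study drug, the subject will be removed from the study". Section 5.3 withdraws subjects after 30 or more days of non-compliance. Section 4.6.2 provides for data collection on withdrawn subjects at 12 months, with their permission.

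Section 6.2.6 is narrower than 8.2.1. It says that drug-related adverse events and pregnancies are monitored, recorded, and reported to the IRB and the company. The primary safety endpoint in section 3.7 is the percentage of patients with adverse events over the 12 months, without regard to cause.

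**The concern.** There are two separate problems.

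The first is that staff have two instructions on which events to record. Under 8.2.1 an event judged unrelated is recorded. On a literal reading of 6.2.6 it is not. Because the primary safety endpoint counts patients with any adverse event, a patient whose only events were judged unrelated would drop out of the numerator. That judgement would then be made at the moment of recording, and the omitted events could not be reviewed later.

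The second is that the 30-day rule has no planned contact behind it. Following a known event to its outcome does not detect a new one, and after visit 5 nobody is scheduled to ask. For subjects who stop early, the 30 days can fall inside the 12 months of the endpoint, so the matter is then more than compliance with 8.2.1.

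**Working it through.** The plan gives no figure on this point, so there is none to reproduce. The check is a comparison of text and a day count.

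**Which events are recorded**

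| Place | Scope |
|---|---|
| 6.2.6 | Drug-related events monitored, recorded and reported |
| 8.2.1 | All events recorded |
| 3.7 | Endpoint counts patients with adverse events, no causality limit |
| Section 6 schedule and Attachment 1 | Unrestricted adverse event row, marked at all 13 time points |
| 6.2.7 | Adverse events reviewed at each monthly contact, unrestricted |
| 8.2.3 | Sets a follow-up rule for events that are not serious, severe or possibly/probably related |
| 1.6.1, 8.6.1.4, 8.6.1.5 | DSMB receives all events, serious or not |
| 8.1.6 | Relatedness scale includes an unlikely category |

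Section 6.2.6 is the only entry with a causality filter. Section 8.1.4 defines a drug reaction as one with a possible or probable relation, so under that filter the unlikely category in 8.1.6 would have no use.

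**Completers**

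Inputs: window of 30 days (8.2.1); visit 5 at 12 months ± 28 days (section 6, 12.4); treatment for 12 months (Study Summary); last monthly contact at month 11 (6.2.7). Let v be the day of visit 5 relative to nominal month 12.

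If dosing ends at 12 months, the days of the window that follow the last contact are 30 − max(v, 0):

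- v ≤ 0: 30 − 0 = 30
- v = +14: 30 − 14 = 16
- v = +28: 30 − 28 = 2

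If dosing runs to visit 5, all 30 days follow it. For a visit 4 weeks early with dosing to 12 months, the time from last contact to the close of the window is 30 + 28 = 58 days. That is elapsed time; the number of post-dose days without a later contact is still 30.

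**Early stoppers**

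Taking 12 months as 365 days, the whole window lies inside the 12 months of 3.7 if the last dose is by day 365 − 30 = 335. The provisions that apply are:

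- 8.2.1 and 8.2.3: known events are followed, and those that are serious, severe or possibly/probably related are followed to recovery, with an allowance for chronic conditions.
- 4.6.1: follow-up care, including clinic follow-up, when necessary.
- 5.3: withdrawal comes after 30 or more days of non-compliance. If those days are consecutive, the window has passed while the subject was still on the normal schedule.
- 8.2.1.5: a subject who becomes pregnant stays in follow-up.
- 4.6.2: collection at month 12, with permission.

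None of these is a scheduled enquiry about new events in the 30 days after the last dose. The gap is therefore new events in subjects who stop with no ongoing event follow-up.

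**The case against.** The strongest case on 6.2.6 is that it does not say only drug-related events count. Its sentence ends with reporting to the IRB and the company, so it can be read as an external-reporting rule, and the next paragraph, the schedule and the DSMB text all collect events without restriction. A reader might infer that 6.2.6 limits recording to drug-related events; the documents do not establish that. What remains is a conflict. The sentence covers monitoring and recording as well as reporting. Even as a reporting rule it is narrower than 8.2.2.2, which sends all SAEs to the company, and 8.6.1.5, under which unexpected serious events are reported regardless of relationship.

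On early stoppers, the objection is that someone who stops for intolerance will usually have a possibly or probably related event already under follow-up, and that 8.2.1 requires questioning at contacts. This stands, and it narrows the point to new events in subjects without such follow-up.

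A reader might also infer that each early stopper loses one scheduled contact in the window. That does not follow. Monthly contacts are 365/12 = 30.4 days apart, so after a last dose at month 1, 3, 6 or 9 the next nominal contact falls 0.4 days outside the 30-day window. Nor can it be said that events in the window would be asked about only at month 12, since event follow-up or clinic care may bring the subject in sooner.

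**Conclusion.** The point holds as two matters to reconcile.

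Section 6.2.6 conflicts with 8.2.1, 3.7 and the other places listed. If followed literally for recording, it under-counts the primary safety endpoint. The documents give no basis for saying by how much, or whether it would be followed that way.

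The 30-day rule has no scheduled contact behind it. For completers, the window is covered only by chance when visit 5 is late: 2 to 30 days follow the last contact if dosing ends at 12 months, and 30 if dosing runs to visit 5. A reader might infer that the planned safety result is therefore wrong for completers. It is not, on the reading that treatment and the 12 months of 3.7 close together: the uncovered days lie after the endpoint, and what goes undelivered is the 8.2.1 rule.

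For early stoppers with a last dose by about day 335, the window lies inside the endpoint period, so new events in those without ongoing follow-up may be missed. This assumes that removal from the study ends calls and visits. Section 4.6.1 says so outright only for removal decided by the investigator. The number of such subjects is not given, and neither a size nor a direction by arm is claimed.

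**What to change.** 1. In 6.2.6, replace the drug-related qualifier with all adverse events. Record relatedness under 8.1.6, and leave external reporting to 8.2.2 and 8.6.1.5.
2. Add one adverse event call or email at 30 days after the last dose to the section 6 schedule, Attachment 1 and 6.2.7. It should apply to completers and to early stoppers who give the permission that 4.6.2 requires.
3. Optionally, state in 4.6.2 that the permitted month-12 collection includes adverse events since the last contact.

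The cost is wording edits, one brief extra contact per subject by staff who already make eight, and slightly more recording. No treatment rule changes.

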8.2.1.4 Hospitalization, Prolonged Hospitalization or Surgery

1082 Any adverse event that results in hospitalization or prolonged hospitalization should be documented and reported as a serious adverse event unless specifically instructed otherwise in this protocol. Any condition responsible for surgery should be documented as an adverse event if the condition meets the criteria for any adverse event.

1085 1086 1087

1088

1089 1090

1091

1092 1093

1094

1095

1096

1076

1077

1078

1079 1080

1081

1083

1084

Neither the condition, hospitalization, prolonged hospitalization, nor surgery are reported as an adverse event in the following circumstances:

- Hospitalization or prolonged hospitalization for diagnostic or elective surgical procedures for a preexisting condition. Surgery should **not** be reported as an outcome of an adverse event if the purpose of the surgery was elective or diagnostic and the outcome was uneventful.
- Hospitalization or prolonged hospitalization required to allow efficacy measurement for the study.
- Hospitalization or prolonged hospitalization for therapy of the target disease of the study, unless it is a worsening or increase in frequency of hospital admissions as judged by the clinical investigator.

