1187 8.3 Liability 1188 The sponsor-investigator will be responsible for the conduct of the study and agrees to defend, indemnify, and hold harmless Novo Nordisk, any of its parent companies, affiliates, or subsidiaries, and their 1189 respective officers, directors, employees, agents, representatives, distributors, salespersons, customers, 1190 licensees, and end-users from and against any claim, suit, demand, loss, damage, expense or liability 1191 imposed by any third party arising from or related to: (a) any breach of sponsor-investigator's obligations 1192 or representations; or (b) sponsor-investigator's negligent or grossly negligent use or willful misuse of the 1193 1194 study drug, the results, or services derived therefrom. This indemnification shall not apply in the event and to the extent that a court of competent jurisdiction or a duly appointed arbiter determines that such 1195 losses or liability arose as a result of Novo Nordisk's gross negligence, intentional misconduct, or 1196 1197 material breach of its responsibilities 1198 8.4 **Unblinding Procedures** 1199 The randomization information will be revealed to the investigator only in a medical emergency, i.e. 1200 when this appears necessary to ensure the subject's safety and would be instrumental in further treatment 1201 decisions. 1202 1203 If a subject's treatment is unblinded, details of the time and reason for revealing must be documented in the subject's medical records and in the CRF and should be reported to DSMB in 48 hours. 1204 1205 8.5 **Stopping Rules** 1206 • The trial will be terminated if two or more patients die within the 30 days of study drug 1207 administration 1208 • The trial will be terminated if during the follow-up period five or more of the first 50 patients 1209 developed gastrointestinal or endocrine disorder leading to inpatient admission. 1210 • The trial will be terminated if the DSMB determine that the study should be terminated. 1211 8.6 **Medical Monitoring** 1212 It is the responsibility of the Principal Investigator to oversee the safety of the study. This safety 1213 monitoring will include careful assessment and appropriate reporting of adverse events as noted above, as well as the construction and implementation of a site data and safety-monitoring plan. 1214 1215 8.6.1 **Data Monitoring Committee** 1216 1217 **Data Safety and Monitoring Board (DSMB)** 1218 8.6.1.1 DSMB Responsibilities Review the research protocol, informed consent documents, and plans for data safety; 1219 1220 Review the following blinded data; baseline data 1221 1222 safety data (mortality and morbidity) o efficacy data 1223 1224 study withdrawal due to non-compliance and AEs major protocol violation 1225 • Review external data to the study when relevant information that may have an impact on 1226 subject safety becomes available; 1227 Review and evaluate ad hoc safety issues concerning the study at the request by study team; 1228

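### Exception 1 of section 8.2.1.4 has no clause for worsening, so it conflicts with the rule in 8.2.1.1 that a worsened pre-existing condition is an adverse event

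*Combined protocol and SAP*

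**What the plan says.** Section 8.1.2 counts as an adverse event anything that appears or gets worse during the study. Section 8.2.1.1 applies this to pre-existing conditions: such a condition should "be recorded as an adverse event if the frequency, intensity, or the character of the condition worsens" during the study period. Section 8.2.1 requires every adverse event in the study period to be recorded.

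Section 8.2.1.4 opens with two general rules. An adverse event that leads to admission is reported as serious unless the protocol specifically instructs otherwise. A condition that leads to surgery is documented as an adverse event if it meets the criteria for one.

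It then gives three exceptions, introduced by "Neither the condition, hospitalization, prolonged hospitalization, nor surgery are reported as an adverse event in the following circumstances". The first is "Hospitalization or prolonged hospitalization for diagnostic or elective surgical procedures for a preexisting condition". The second covers admissions needed for efficacy measurement. The third covers admissions for treatment of the target disease, and it does not apply where the investigator judges that there has been a worsening or more frequent admission.

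Section 3.7 defines the primary safety endpoint as the percentage of patients with adverse events over the 12 months.

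**The concern.** The lead-in to the exceptions removes the condition itself from reporting, as well as the admission and the surgery. Exception 1 then applies to any pre-existing condition, stable or worse, provided the admission is for a diagnostic or elective surgical procedure. That takes in cases which 8.2.1.1 says must be recorded.

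The result is also perverse. A worsened condition managed without admission falls outside exception 1 and is plainly an adverse event under 8.2.1.1. The same worsening, if it leads to a planned admission, could go unrecorded. The exemption bites on the cases that would otherwise be candidates for a serious adverse event.

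Safety in this population is a stated objective. Eligible subjects may enter with conditions that can worsen. Type 2 diabetes not treated with insulin and hypertension are allowed, and apart from biliary disease and a history of pancreatitis the exclusion list in 4.4 names no gastrointestinal condition. If the drug worsens such conditions, any events lost would fall more in the liraglutide arm. If it does not, both arms would be understated.

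**Working it through.** There is no figure in the plan to reproduce and no arithmetic to apply. The check is to apply each section to one hypothetical case: a subject has a gastrointestinal complaint noted at screening, it becomes more frequent after the first dose, and the subject is admitted for a planned diagnostic procedure.

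1. **Section 8.1.2.** The complaint has worsened during the study, so it is an adverse event.
2. **Section 8.2.1.1.** Its frequency has increased, so it should be recorded as an adverse event.
3. **Section 8.2.1.4, opening rules, with 8.1.3.** An adverse event that leads to admission is serious, unless the protocol specifically says otherwise.
4. **Section 8.2.1.4, exception 1.** The condition is pre-existing, there is a hospital admission, and the purpose is diagnostic. Every term of the exception is met, so neither the condition nor the admission is reported as an adverse event.

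Steps 1 to 3 and step 4 give opposite answers. Three places might break the tie:

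- **The opening rule on admissions.** It gives way to specific instructions elsewhere in the protocol, and the exceptions are such instructions. It cannot be relied on to override them.
- **Exception 3.** It contains an explicit clause for worsening. Exception 1, in the same list, has none. Someone applying the list could reasonably take the difference as intended.
- **Cross-references.** Section 8.2.1.1 does not mention the exceptions, and 8.2.1.4 does not mention 8.2.1.1. Neither states which prevails.

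The consequences differ by measure:

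- **Primary safety endpoint (3.7).** This is a patient-level proportion. A patient's status changes only if the omitted event was that patient's only adverse event. Section 1.6.1 lists nausea alone at 39.3%, so many liraglutide subjects are likely to be counted anyway and the effect on this endpoint is diluted.
- **Serious adverse event count.** Here there is no such dilution. Each admission that would have made a worsened condition serious, and that is exempted, removes one event.

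For an event to be lost, the condition must be pre-existing, it must have worsened, the subject must be admitted, and the admission must be for a diagnostic or elective procedure. The documents give no frequency for this combination, so the number lost cannot be calculated.

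**The case against.** The strongest reply is that exception 1 never says it covers worsened conditions. That reach comes from its silence. On an ordinary reading it is aimed at stable conditions with procedures planned anyway, while 8.2.1.1 deals specifically with worsening, and the opening of 8.2.1.4 repeats that a condition leading to surgery is documented if it meets the adverse event criteria. On that reading nothing is lost.

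This is a fair reading, and it is why the point is a conflict on the face of the text and not a demonstrated loss of data. It does not remove the conflict. The lead-in names the condition expressly, exception 3 shows that the drafters wrote a worsening clause where they wanted one, and the opening rule on admissions is subordinate to the exceptions.

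Two stronger readings are tempting and are not supported.

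- **New events treated by elective surgery.** A reader might infer that these are also kept out of the record, because surgery is not to "be reported as an outcome of an adverse event if the purpose of the surgery was elective or diagnostic and the outcome was uneventful". That sentence presupposes a recorded adverse event, and it sits inside the pre-existing-condition bullet. It bars only listing the operation as the outcome. Surgery is not an outcome category in 8.1.7 in any case, and recovery through surgical treatment falls under recovered. Newly arising gallstones, for example, remain an adverse event under 8.1.2, and a serious one if they lead to admission.
- **The stopping rule.** A reader might infer that the stopping count in 8.5 is lowered. That rule counts patients among the first 50 who "developed gastrointestinal or endocrine disorder leading to inpatient admission". It is worded by disorder and admission, not by adverse event status, so 8.2.1.4 does not by its terms change it. It also speaks of disorders that developed, whereas exception 1 concerns conditions already present. Section 9.3 lists hospital records among the examples of source documents, so admissions need not be known only through adverse event reports.

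**Conclusion.** The point holds as an internal inconsistency. Exception 1 of 8.2.1.4, read with its lead-in, conflicts with 8.2.1.1 and 8.1.2 for a worsened pre-existing condition that leads to a diagnostic or elective admission, and nothing in the protocol clearly resolves it.

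Followed literally, exception 1 could leave some events out of the primary safety endpoint and the serious adverse event count. This assumes that whoever records events applies the exception as written and does not defer to 8.2.1.1. The size is unknown. An under-count is possible, not shown. The primary efficacy analysis is not affected.

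**What to change.** Add to the end of exception 1 in 8.2.1.4: *that has not worsened in frequency, intensity or character since screening (see 8.2.1.1)*. A worsened pre-existing condition that leads to admission would then be recorded as an adverse event and assessed for seriousness, as 8.2.1.1 and the opening of 8.2.1.4 already imply. No change to the surgery sentence or to 8.5 is needed for this purpose.

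The cost is one clause of protocol wording and at most a few more adverse event or serious adverse event reports. If any admission has already been left unreported under exception 1, it should be checked against the amended wording from the source documents. The change concerns recording only and does not touch treatment or clinical management.
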